4.1.3 Exclusion Criteria

Deviations from exclusion criteria are not allowed because they can potentially jeopardise the scientific integrity of the study, regulatory acceptability or subject safety. Therefore, adherence to the criteria as specified in the protocol is essential.

Subjects meeting any of the following criteria must not be enrolled in the study:

1. Primary mucosal or ocular melanoma.
2. Prior treatment with a BRAF inhibitor (including but not limited to dabrafenib, vemurafenib, LGX818, and XL281/BMS-908662) or a MEK inhibitor (including but not limited to trametinib, AZD6244, and RDEA119). Any major surgery, extensive radiotherapy, chemotherapy with delayed toxicity, biological anti-cancer therapy, or immunol anti-cancer therapy within 21 days prior to enrollment /or daily or weekly chemotherapy without the potential for delayed toxicity within 14 days prior to enrollment. . (Note: Ipilimumab, pembrolizumab and nivolumab treatment must have ended at least 8 weeks prior to enrollment).
3. Taken an investigational drug within 28 days or 5 half-lives (minimum 14 days), whichever is shorter, prior to enrollment(Note: in case ipilimuamb, pembrolizmab and nivolumab are investigational drug in the regions and countries, and in case of PD-L1 antibody, these investigational treatment shall be ended at least 8 weeks prior to enrollment).
4. Current use of a prohibited medication (See Section 6.1).
5. Known immediate or delayed hypersensitivity reaction or idiosyncrasy to drugs chemically related to the study treatments, their excipients, and/or dimethyl sulfoxide (DMSO).
6. A history of Hepatitis B Virus (HBV), or Hepatitis C Virus (HCV) infection (subjects with laboratory evidence of cleared HBV and/or HCV will be permitted, which is defined as HBs antigen negative and HBV DNA negative(≤1000 copies/mL) and HCV antibody is negative).

7. Leptomeningeal or brain metastases or metastases causing spinal cord compression that are: symptomatic or untreated or not stable for ≥ 3 months (must be documented by imaging before inclusion and compare with the latest brain scan prior to the one for the inclusion) or requiring corticosteroids. Subjects on a stable dose of corticosteroids > 1 month, or on replacement dose only, or have been off of corticosteroids for at least 2 weeks can be enrolled with approval of the Novartis Medical Lead. Subjects must also be off of enzyme-inducing anticonvulsants for > 4 weeks.
8. History of malignancy other than disease under study within 3 years, of study enrolment with exceptions below.

Exception: Subjects with a history of completely resected non-melanoma skin cancer, or subjects with indolent second malignancies are eligible only after the approval of the sponsor's Medical Lead.
9. History of malignancy with confirmed activating RAS mutation at any time. Note: Prospective RAS testing is not required. However, if the results of previous RAS testing are known, they must be used in assessing eligibility.
10. Any serious or unstable pre-existing medical conditions (aside from malignancy exceptions specified above), psychiatric disorders, or other conditions that could interfere with the subject's safety, obtaining informed consent, or compliance with study procedures.
11. A history or evidence of cardiovascular risk including any of the following:
 - a. Current LVEF $<$ Institutional LLN
 - b. A QTc interval corrected for heart rate ≥ 480 msec (using Bazett's formula; see [Appendix 3](#) for correction methods)
 - c. A history or evidence of current clinically significant uncontrolled arrhythmias;
Clarification: Subjects with atrial fibrillation controlled for > 30 days prior to dosing are eligible.
 - d. A history of acute coronary syndromes (including myocardial infarction or unstable angina), coronary angioplasty, or stenting within 6 months prior to randomization;
 - e. A history or evidence of current \geq Class II congestive heart failure as defined by the New York Heart Association (NYHA) guidelines ([Appendix 4](#));
 - f. Patients with intra-cardiac defibrillators;
 - g. Treatment refractory hypertension defined as a blood pressure of systolic > 140 mmHg and/or diastolic > 90 mm Hg which cannot be controlled by anti-hypertensive therapy;
 - h. Abnormal cardiac valve morphology (\geq grade 2) documented by echocardiogram (subjects with grade 1 abnormalities [i.e., mild regurgitation/stenosis] can be entered on study). Subjects with moderate valvular thickening should not be entered on study.

12. Uncorrectable electrolyte abnormalities (e.g. hypokalaemia, hypomagnesaemia, hypocalcaemia determined by blood chemistry), long QT syndrome or taking medicinal products known to prolong the QT interval.
13. A history or current evidence of retinal vein occlusion (RVO)
14. [Retired from protocol version 03]
15. [Retired from protocol version 03]
16. Pregnant or nursing females.
17. History of or current diagnosis of interstitial lung disease or pneumonitis.

4.2 Permanent Discontinuation from Study Treatment and Study Completion Criteria

4.2.1 Permanent Discontinuation from Study Treatment

Subjects will receive study treatment until disease progression, death, or unacceptable AE, including hematologic or other non-hematologic toxicity, and/or meeting stopping criteria for liver chemistry defined in Section 5.9. Note: Subjects who are experiencing progression of disease (by RECIST, version 1.1) but are receiving clinical benefit based on the investigator's assessment, may be allowed to continue study treatment (see Section 4.2.2) with the agreement of sponsor's Medical Lead.

In addition, study treatment may be permanently discontinued for any of the following reasons:

- a. deviation(s) from the protocol
- b. request of the subject or his/her proxy
- c. investigator's discretion
- d. subject is lost to follow-up, (defined as no contact with the subject after 3 telephone calls and one certified letter to the last known address, and documented in the patient's chart)
- e. study is completed or terminated.

The primary reason study treatment was permanently discontinued must be documented in the subject's medical records and electronic case report form (eCRF).

If the subject voluntarily discontinues from treatment due to toxicity, 'adverse event' will be recorded as the primary reason for permanent discontinuation in the eCRF.

Note: If one study drug is permanently discontinued, administration of the other study drug may continue if appropriate (see Section 5.8), and subjects should be assessed as indicated in the Time and Events Table (see Section 7).

All subjects who permanently discontinue all study treatment will have safety assessments at the time of discontinuation and during post-study treatment follow-up as specified in the Time and Events Table (Table 20) and Section 7.

All subjects who permanently discontinue all study treatment without disease progression will be followed for progression according to the Time and Events Table (Table 20) until disease progression, death, or withdrawal of consent, whichever occurs first.

In addition, all subjects who permanently discontinue all study treatment will be followed for survival and new anti-cancer therapy according to the Time and Events Table (Table 20). Follow-up contact to assess survival and new anti-cancer therapy may be made via clinic visit, phone, or email.

Survival and new anti-cancer therapy follow-up will continue until study completion.

4.2.2 Continuation of Study Treatment after Disease Progression

Subjects may be eligible to continue study treatment after disease progression if they have:

- Achieved an objective response (partial or complete response) according to RECIST, version 1.1, or have had stable disease with imaging evidence of tumor reduction lasting at least 8 weeks prior to disease progression while receiving study treatment
- No treatment-related AEs of CTCAE grade 4 during the last four weeks of study treatment
- No signs and symptoms of clinical disease progression that decrease ECOG performance status to ≥ 2
- No severe clinical conditions that require immediate surgical or radiotherapeutical intervention. Note: subjects who require palliative radiation of bone lesions or limited surgical removal of isolated tumor lesions may be considered after completion of the procedure (radiotherapy or surgery) and review by the Novartis Medical Lead.

If all of the above conditions are met, the following steps must be implemented prior to continuation of study treatment:

- **The investigator must consult with and receive approval from the Novartis Medical Lead**
- **The subject must sign an informed consent that specifies alternative therapies (e.g., FDA-approved therapies) that the subject may be foregoing by continuing study treatment**

After a subject has been permitted to continue on study treatment:

- All study procedures, including tumor assessments, must be followed as scheduled (Table 20)
- After each tumor assessment, the investigators must confirm with the Novartis Medical Lead that the subject is still benefitting from study treatment and therefore can continue receiving study treatment.

4.2.3 Subject Completion Criteria

A subject will be considered to have completed the study if the subject dies during the study treatment or follow-up period. The cause of death will be documented in the eCRF. A subject will be considered to have withdrawn from the study if the subject has not died and is lost to

follow-up or has withdrawn consent, or if the study is completed. The definition of study completion was described in protocol Section 3.1.

5 Study treatments

The term ‘study treatment’ is used throughout the protocol to describe any combination of products received by the subject as per the protocol design. Study treatment may therefore refer to the individual study treatments or the combination of those study treatments.

5.1 Investigational Product and Other Study Treatment

5.1.1 Dabrafenib (GSK2118436)

Dabrafenib will be provided as 50 mg and 75 mg capsules. Each capsule will contain 50 mg or 75 mg of free base (present as the [REDACTED]).

Dabrafenib will be provided to sites by Novartis with the exception of sites in China where GSK will organize to provide supplies under GSK’s sponsorship. The contents of the label will be in accordance with all applicable regulatory requirements.

5.1.2 Trametinib (GSK1120212)

Trametinib study medication will be provided as 0.5 mg and 2.0 mg tablets. Each tablet will contain 0.5 mg or 2.0 mg of trametinib parent (present as the [REDACTED]).

Trametinib will be provided to sites by Novartis with the exception of sites in China where GSK will organize to provide supplies under GSK’s sponsorship. The contents of the label will be in accordance with all applicable regulatory requirements

5.2 Dosage and Administration

- Dabrafenib, 150 mg, BID;
- Trametinib, 2.0 mg, once daily.

When administered in combination with trametinib, take the once-daily dose of trametinib at approximately the same time each day with either the morning dose or the evening dose of dabrafenib. The second dose of dabrafenib (150 mg) should be administered approximately 12 hours after the morning dose. Study medication should be taken orally with approximately 200 mL of water under fasting conditions, either 1 hour before or 2 hours after a meal.

If a subject vomits after taking study medication, the subject should be instructed not to retake the dose and should take the next dose as originally scheduled.

If administration of trametinib is interrupted or permanently discontinued, administration of dabrafenib may be continued. If administration of dabrafenib is interrupted, or permanently discontinued, administration of trametinib may continue.

If a subject misses a dose of dabrafenib, the subject may take the dose immediately if the next dose is scheduled for at least 6 hours later. If the next scheduled dose of dabrafenib is due in less than 6 hours, the subject should skip the dose and resume of dabrafenib dosing at the next scheduled dose

If a subject misses a trametinib dose, the subject may take the dose immediately if the next dose is scheduled for at least 12 hours later.

5.3 Handling and Storage of Study Treatments

Dabrafenib and trametinib must be dispensed and administered in accordance with the protocol, and only to subjects enrolled in the study. Dabrafenib and trametinib must be stored in a secure area under the appropriate physical conditions for the product. Study medication is to be stored at the temperature specified on the label. Maintenance of a temperature log (manual or automated) is required. Access to and administration of dabrafenib and trametinib will be limited to the investigator and authorized site staff.

Procedures for final disposition of unused study treatments will be provided in the SPM.

5.4 Treatment Assignment

This is a single arm, open label study. All subjects enrolled will receive the combination of dabrafenib and trametinib.

Subjects will be identified by a unique subject number that will remain consistent for the duration of the study.

All subjects will be registered into the My Access Program (MAP) system, by the investigator or authorized site staff.

MAP allows study sites to register subjects, and also is used in study treatment supply.

Detailed MAP user instructions, worksheets, and telephone contact numbers will be provided to the study site.

5.5 Blinding

This is an open-label, single-arm study.

5.6 Product Accountability

In accordance with local regulatory requirements, the investigator, designated site staff, or head of the medical institution (where applicable) must document the amount of investigational product dispensed and/or administered to study subjects, the amount returned by study subjects, and the amount received from and returned to Novartis, when applicable. Product accountability records must be maintained throughout the course of the study. Refer to the SPM for further detailed instructions on product accountability.

5.7 Treatment Compliance

Subjects will be instructed to return treatment bottles at each visit. Compliance with study treatment will be assessed by querying the subject and thorough pill count at each visit. Compliance will be documented in the source documents and the eCRF.

A record of the number of dabrafenib and trametinib capsules/tablets dispensed to and taken by each subject must be maintained and reconciled with study treatment and compliance records. Treatment start and stop dates, including dates of dose modifications and/or interruptions will also be recorded in the eCRF. The investigator will make every effort to bring non-compliant subjects into compliance.

5.8 Dose Modification Guidelines

The severity of adverse events will be graded utilizing the CTCAE v4.0. Guidelines for dose modifications and interruptions for management of common toxicities associated with the study treatment are provided in this section.

Dose modifications in response to adverse events are permitted. Dose modification guidelines include:

- general guidelines for clinically significant toxicities related to study treatments and
- specific guidelines for adverse events of special interest, which are events that have been observed with higher frequency or severity in subjects receiving dabrafenib, trametinib, or a combination of both therapies.

With the exceptions of pyrexia (likely related to dabrafenib) and LVEF (likely related to trametinib), the guidance suggests that both therapies be reduced simultaneously in response to toxicities that are considered by the investigator to be treatment related.

Table 3 Categories of Dose Modification Guidelines

Adverse Event	Dabrafenib	Trametinib	Section
General Guidelines for Clinically Significant Toxicities	X	X	5.8.2
Guidelines for Specific Adverse Events			
Cardiovascular Adverse Events			
LVEF		X	5.8.3.1
Hypertension	X	X	5.8.3.2
Prolonged QTc	X	X	5.8.3.3
Skin –Related Adverse Events (Except cuSCC) ^a			
Rash	X	X	5.8.4.1
Hand-Foot Skin Reaction	X	X	5.8.4.2
Other Adverse Events			
Pyrexia	X		5.8.5.1
Diarrhea	X	X	5.8.5.2
Renal Insufficiency	X	X	5.8.5.3
Visual Changes	X	X	5.8.5.4
Pneumonitis	X	X	5.8.5.5
Liver Chemistry Stopping Criteria	X	X	5.9.1

a. Refer to Section [5.8.4.4](#) for management of cuSCC

5.8.1 Dose Levels of dabrafenib and trametinib

The dose levels for this study are provided in [Table 4](#).

Table 4 Dose Level Reduction Guidelines

Dose Level	Dabrafenib Dose/Schedule	Trametinib Dose/Schedule
Starting Dose	150 mg BID	2 mg once daily
-1 (1 st Dose reduction)	100 mg BID	1.5 mg once daily
-2 (2 nd Dose reduction)	75 mg BID	1.0 mg once daily

Abbreviation: BID = twice daily

Re-escalation of dose levels is permitted if an AE resolves to grade 1 or baseline at the reduced dose level, and no additional toxicities are seen after 4 weeks of study treatment at the reduced dose.

A dose reduction below 75 mg BID for dabrafenib or below 1 mg once daily for trametinib is not allowed. If a dose reduction below 75 mg BID for dabrafenib is required, dabrafenib will be permanently discontinued but these subjects will be allowed to continue trametinib.

If a dose reduction below 1.0 mg once daily for trametinib is required, then trametinib will be permanently discontinued, but these subjects will be allowed to continue dabrafenib.

Note: Approval from the Novartis Medical Lead is required to restart study treatment after ≥21 days of interruption. Study drug must be discontinued permanently if any interruption goes beyond 26 weeks.

5.8.2 General Guidelines for Clinically Significant Toxicities

The below [Table 5](#) presents general guidelines regarding management and dose reduction for adverse events that are considered by the investigator to be related to study treatment and which do not have specific guidelines listed in [Table 3](#).

Table 5 General Dose Modification Guidelines for Events Considered Related to Study Treatment

CTCAE Grade ¹	Action and Dose Modification
Grade 1	
 Continue study treatment at current dose level Monitor closely Provide supportive care according to institutional standards
Grade 2	
 Interrupt study treatment if clinically indicated Monitor closely Provide supportive care according to institutional standards When toxicity resolves to grade 1 or baseline, restart study treatment at current dose level
Grade 3	
 Interrupt study treatment Monitor closely Provide supportive care according to institutional standards When toxicity resolves to grade 1 or baseline, restart study treatment reduced by one dose level If the grade 3 toxicity recurs, interrupt study treatment When toxicity resolves to grade 1 or baseline, restart study treatment reduced by another dose level
Grade 4	
 Interrupt study treatment Monitor closely Provide supportive care according to institutional standards Restart with study treatment reduced by one dose level once toxicity resolves to grade 1 or baseline If the grade 4 toxicity recurs, either permanently discontinue study treatment or, if the subject is clinically benefiting, discuss continuation of study treatment with the Novartis Medical Lead.

- Adverse events assessed by clinical laboratory parameters, adverse events, cardiac parameters, and vital signs according to the Common Terminology Criteria for Adverse Events version 4 (CTCAE v4.0).

5.8.3 Guidelines for Cardiovascular Adverse Events

Cardiovascular adverse events have been seen in subjects receiving either dabrafenib, trametinib or both in combination (see the trametinib, dabrafenib and combination IBs for additional information).

5.8.3.1 Left Ventricular Ejection Fraction (LVEF)

Decreases of the left-ventricular-ejection-fraction (LVEF) have been observed in subjects receiving trametinib monotherapy and in combination with dabrafenib. Therefore, ECHOs must be performed to assess cardiac ejection fraction in regular intervals as outlined in the Time and Events Table ([Table 20](#)). All ECHOs will be collected; instructions are provided in

the Study Procedures Manual (SPM). Dose modification guidance and stopping criteria for LVEF decrease are provided in [Table 6](#).

Table 6 Dose Modification Guidelines and Stopping Criteria for LVEF Decrease

Clinic	LVEF-drop (%) or CTCAE grade	Action and Dose Modification
Asymptomatic	Absolute decrease of >10% in LVEF compared to baseline and ejection fraction below the institution's low LLN	
 • Interrupt trametinib and repeat ECHO within 2 weeks^{a,b} • If the LVEF recovers within 4 weeks (defined as LVEF ≥LLN and absolute decrease ≤10% compared to baseline) 
 ○ Consult with the Novartis Medical Lead and request approval for restart ○ If approve, restart treatment with trametinib reduced by one dose level ○ Repeat ECHO at 2, 4, 8 and 12 weeks after re-start; continue in intervals of 12 weeks thereafter • If repeat LVEF does not recover within 4 weeks 
 ○ Consult with cardiologist ○ Permanently discontinue trametinib ○ Report as SAE ○ Repeat ECHO after 2, 4, 8, 12, and 16 weeks or until resolution
Symptomatic ^c	Grade 3: resting LVEF 39-20% or >20% absolute reduction from baseline	
 • Permanently discontinue trametinib^b • Interrupt dabrafenib.^d • Report as SAE • Consult with cardiologist • Repeat ECHO after 2, 4, 8, 12, and 16 weeks or until resolution^{b,d}
	Grade 4: resting LVEF <20%	

Abbreviations: CTCAE = Common Terminology Criteria for Adverse Events; ECHO = echocardiogram; LLN = lower limit of normal; LVEF = left ventricular ejection fraction;

- a. If ECHO does not show LVEF recovery after 2 weeks, repeat ECHO 2 weeks later.
- b. If recurrent episodes of LVEF reduction occur in subjects receiving dabrafenib monotherapy, consult Novartis Medical Lead.
- c. Symptoms may include: dyspnea, orthopnea, and other signs and symptoms of pulmonary congestion and edema.
- d. Once LVEF recovers, including resolution of symptoms, restart of dabrafenib monotherapy only can be considered in consultation with Novartis Medical Lead.

5.8.3.2 Hypertension

Increases in blood pressure have been observed in subjects receiving trametinib. Recommendations for blood pressure monitoring and management are provided in Section [5.8.3.2.1](#) and Section [5.8.3.2.2](#).

5.8.3.2.1 Monitoring of Hypertension

All blood pressure assessments should be performed under the following optimal conditions:

- the subject has been seated with back support, ensuring that legs are uncrossed and flat on the floor
- the subject is relaxed comfortably for at least 5 minutes
- restrictive clothing has been removed from the cuff area and the right cuff size has been selected
- the subject's arm is supported so that the middle of the cuff is at heart level
- the subject remains quiet during the measurement.

In subjects with an initial blood pressure reading within the hypertensive range, a second reading should be taken at least 1 minute later, with the 2 readings averaged to obtain a final blood pressure measurement. The averaged value should be recorded in the eCRF.

Persistent hypertension is defined as an increase of systolic blood pressure (SBP) > 140 mm Hg and/or diastolic blood pressure (DBP) > 90 mm Hg in three consecutive visits with blood pressure assessments from two readings collected as described above. Visits to monitor increased blood pressure can be scheduled independently from the per-protocol visits outlined in the Time and Events Table ([Table 20](#)). Ideally, subsequent blood pressure assessments should be performed within one week.

Asymptomatic hypertension is defined as an increase of SBP >140 mm Hg and/or DBP >90 mm Hg in the absence of headache, light-headedness, vertigo, tinnitus, episodes of fainting or other symptoms indicative of hypertension.

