5.8.3.2.2 Management of Hypertension

For subjects experiencing an increase in systolic and/or diastolic blood pressure that is persistent and may be associated with the study treatment, recommendations for the clinical management of hypertension are described below in [Table 7](#).

Table 7 Management and Dose Modification Guidelines for Hypertension

Hypertension	Action and Dose Modification
(Scenario A) 
 • Asymptomatic and persistent^a SBP of ≥ 140 and < 160 mmHg, or DBP ≥ 90 and < 100 mmHg, or 
 • Clinically significant increase in DBP of 20 mmHg (but still below 100 mmHg). 	
 • Continue study treatment at the current dose • Adjust current or initiate new antihypertensive medication • Titrate antihypertensive medication(s) during the next 2 weeks as indicated to achieve well-controlled^b BP • If BP is not well controlled within 2 weeks, consider referral to a specialist and go to scenario (B).
(Scenario B) 
 • Asymptomatic SBP ≥ 160 mmHg, or DBP ≥ 100 mmHg, or 
 • Failure to achieve well-controlled BP within 2 weeks in Scenario A 	
 • Interrupt study treatment if clinically indicated • Adjust current or initiate new antihypertensive medication(s) • Titrate antihypertensive medication(s) during the next 2 weeks as indicated to achieve well-controlled BP • Once BP is well controlled^b, restart study treatment reduced by one dose level
or 
 • Symptomatic^c hypertension • Persistent SBP ≥ 160 mmHg, or DBP ≥ 100 mmHg, despite antihypertensive medication and dose reduction of study treatment 	
 • Interrupt study treatment • Adjust current or initiate new antihypertensive medication(s) • Titrate antihypertensive medication during the next 2 weeks as indicated to achieve well-controlled BP • Referral to a specialist for further evaluation and follow-up is recommended • Once BP is well controlled, restart study treatment reduced by one dose level
Refractory hypertension unresponsive to above interventions or hypertensive crisis.	
 • Permanently discontinue study treatment • Continue follow-up per protocol.

BP = blood pressure; DBP = diastolic blood pressure; mmHg = millimetres mercury; SBP = systolic blood pressure;

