- a. Hypertension detected in two separate readings during up to three consecutive visits
- b. Well-controlled blood pressure defined as SBP ≤ 140 mm Hg and DBP ≤ 90 mm Hg in two separate readings during up to three consecutive visits.
- c. Symptomatic hypertension defined as hypertension aggravated by symptoms (e.g., headache, light-headedness, vertigo, tinnitus, episodes of fainting) that resolve after the blood pressure is controlled within the normal range.

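### Persistent hypertension is defined in two ways, in Section 5.8.3.2.1 and in Table 7 footnote a, so the same readings can enter Scenario A under one and later, or not at all, under the other; the Scenario A and well-controlled ranges also overlap at exactly 140 and 90 mmHg

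*Protocol*

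**What the plan says.** Section 5.8.3.2.1 sets out the measurement. When a first reading is in the hypertensive range, a second is taken at least 1 minute later and the two are averaged; "The averaged value should be recorded in the eCRF". The section then gives the threshold, "Persistent hypertension is defined as an increase of systolic blood pressure (SBP) > 140 mm Hg and/or diastolic blood pressure (DBP) > 90 mm Hg", and the duration, "in three consecutive visits with blood pressure assessments from two readings collected as described above". Extra visits outside the schedule are allowed, with rechecks ideally within a week.

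Section 5.8.3.2.2 introduces Table 7 for an increase in pressure "that is persistent and may be associated with the study treatment". Scenario A covers asymptomatic and persistent "SBP of ≥ 140 and < 160 mmHg, or DBP ≥ 90 and < 100 mmHg". There the word persistent carries footnote a: "Hypertension detected in two separate readings during up to three consecutive visits". Footnote b sets the treatment target: "Well-controlled blood pressure defined as SBP ≤ 140 mm Hg and DBP ≤ 90 mm Hg in two separate readings", again within up to three visits.

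Scenario A leaves the dose unchanged, calls for antihypertensives to be started or adjusted, and passes to Scenario B if control is not reached in 2 weeks. In Scenario B, interruption is left to clinical indication, and restart is one dose level lower.

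**The concern.** One term, used as the trigger for one table, has two definitions in adjoining subsections. A site following the text and a site following the footnote can place the same subject differently: one starts antihypertensive treatment and the 2-week count, while the other is still waiting or never starts. Table 3 marks hypertension for both drugs, so the pathway bears on the dosing of each. Section 3.1 allows no waivers and requires adherence, which presumes a rule that can be read in only one way.

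The ranges raise a second, smaller problem. Section 5.8.3.2.1 uses strict inequalities, Scenario A includes the boundary values, and footnote b includes them too, on the controlled side. A subject sitting on the boundary therefore qualifies for Scenario A while already at its target.

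At stake are consistent safety management between sites and, further downstream, whether hypertension-related dose changes follow from one trigger or two.

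**Working it through.** The plan states no figure to reproduce. The check applies each rule to the same readings.

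**Persistence.** Call a visit H if hypertensive and N if not, with a gap of *g* days between visits and the first H visit on day 0. Footnote a does not say whether its two readings may fall at one visit, so both readings of it are shown.

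For sustained hypertension (HHH):
- Section 5.8.3.2.1 is met at the third visit: day 2*g*.
- Footnote a, readings at two visits, is met on day *g*. Gap = 2*g* − *g* = *g*.
- Footnote a, two readings at one visit, is met on day 0. Gap = 2*g* − 0 = 2*g*.

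| Visit gap | Section met | Footnote a met (two visits / one visit) | Difference |
|---|---|---|---|
| 3 days | day 6 | day 3 / day 0 | 3 to 6 days |
| 7 days | day 14 | day 7 / day 0 | 1 to 2 weeks |
| 28 days | day 56 | day 28 / day 0 | 4 to 8 weeks |

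The 7-day row is the recheck interval that Section 5.8.3.2.1 calls ideal. The 28-day row assumes that the single on-treatment mark for vital signs in Table 20 belongs to the 4-weekly column; the extracted table does not show this with certainty. The 3-day row is an illustration of closer checks.

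For interrupted sequences, even on the two-visit reading of footnote a:

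| Pattern | Footnote a | Section 5.8.3.2.1 |
|---|---|---|
| HHN | met at visit 2 | not met |
| HNH | met at visit 3 | not met |
| NHH | met at visit 3 | not met within the three visits |
| HHNHHH | met at visit 2 | met at visit 6 |

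Every sequence of up to eight visits that meets the section also meets footnote a, no later. The definitions are nested, with the section the stricter.

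**Thresholds.** Section: SBP > 140 or DBP > 90. Scenario A: 140 ≤ SBP < 160 or 90 ≤ DBP < 100. Footnote b: SBP ≤ 140 and DBP ≤ 90. Each pair below is taken as repeated often enough to satisfy the reading counts.

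| SBP/DBP | Hypertensive (section) | Scenario A range | Well controlled (footnote b) |
|---|---|---|---|
| 139/89 | no | no | yes |
| 140/80 | no | yes | yes |
| 130/90 | no | yes | yes |
| 140/90 | no | yes | yes |
| 141/80 | yes | yes | no |
| 140/95 | yes | yes | no |
| 150/90 | yes | yes | no |

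The overlap consists only of pairs with SBP exactly 140 or DBP exactly 90 and the other component at or below its limit. Those subjects meet footnote b, so they would not pass to Scenario B for failure of control. The overlap therefore adds nothing to the delays above.

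**Record.** Averages at three visits show whether the section's rule was met. If footnote a can be met by two readings at one visit, the single averaged value would not show that it was.

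**The case against.** The best defence is that these are recommendations for investigators, limited to increases that may be related to treatment. Judgement would vary between sites even with a single definition. Extra visits are permitted and encouraged within a week, so the longer gaps need a site to rely on scheduled visits alone. Same-visit readings are averaged into one measurement, so the footnote's separate readings may well mean separate visits, which halves the gap. All of this stands as a limit on size. None of it removes the conflict: a phrase allowing up to three visits still allows fewer than three, and room for judgement does not explain two meanings of one term.

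Several stronger readings that a reader might infer are not supported:

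- **That about 14 subjects are affected** (22% × 65 = 14.3). The 22% in Section 1.2.3 is hypertension of any kind on the combination in another trial. The conflict reaches the dose mainly through asymptomatic subjects in the Scenario A range who then fail 2 weeks of titration. The direct Scenario B criterion and the symptomatic row carry no footnote a.
- **That entry to Scenario B is at 2 weeks under one rule and 10 under the other.** This adds Scenario A's 2 weeks to day 0 and to day 56 (0 + 2 against 8 + 2 weeks). It pairs the most lenient reading of the footnote with 4-weekly visits only. Interruption in Scenario B is also conditional on clinical indication.
- **That Scenario B contradicts the row after it.** The following row's mention of a prior dose reduction is an entry condition. A subject not yet reduced does not meet it and stays in Scenario B.
- **That the dose-change data cannot be interpreted.** SAP Section 2.4.1.4 summarises dose changes with their recorded reasons. SAP Table 2-5 uses its own blood-pressure criteria. No SAP analysis uses the terms persistent or well controlled.

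**Conclusion.** The point holds as an inconsistency in the current protocol text. Persistent hypertension has two nested definitions that classify the same readings differently, and neither document says which governs. The difference in entry to Scenario A depends on how often pressure is checked and on whether footnote a means two visits (the lower figure of each range) or one visit (the higher). For sequences such as high-high-normal the difference is entry against no entry.

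The overlap at exactly 140 or 90 is a separate defect. It affects whether antihypertensives are started in a subject already at target, and not progression to Scenario B.

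The documents do not allow the number of affected subjects to be estimated. The study is single-arm and estimates ORR, and nothing here bears on that estimate. The matter is one of safety management and of consistency between sites, and is worth correcting on those grounds.

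**What to change.** Reconcile Section 5.8.3.2.1 with Table 7 and its footnotes:

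1. Use one definition of *persistent* in both places, stating the number of visits, the number of readings, and whether two readings at one visit count.
2. Make the Scenario A and well-controlled ranges mutually exclusive at 140 and 90, and consistent with the threshold in Section 5.8.3.2.1.
3. Align what the eCRF records with the definition kept. If separate readings at one visit are to count, the average alone is not enough.

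The choice of definition and thresholds belongs to the sponsor. The cost is wording in one section, one table row and two footnotes, with no added visits or procedures; an eCRF change arises only if individual readings are needed. The SAP gives the last patient's last visit as 19-Apr-2021. If the protocol is no longer open to amendment, a note in the study report beside the hypertension-related dose changes, stating that two definitions were in force, would serve instead.
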